Specific aims:

Primary aims:

- Stage 1: To understand postoperative urologic, sexual, and pelvic floor experiences of transgender women
- Stage 2: To validate a questionnaire measuring the frequency and severity of postoperative urogynecologic symptoms in transgender women

Secondary aims:

- To understand the types of urologic, sexual and pelvic floor complaints and their degree of bother
- To evaluate the relationship between procedure technique and symptomatology
- To understand the temporal impact on symptomatology after surgery
- To assess the impact of hormonal therapy or other gender confirming treatments on urologic and pelvic floor symptoms.

Background/significance:

It has been estimated that approximately 1 in 60000 individuals globally suffer from gender dysphoria with male-to-female (MTF) gender dysphoria being 4 times more common than female-to-male (FTM) (1). Oftentimes, these individuals are subjected to social stigmatization, abuse, and a general lack of support, leading to depression and higher than average rates of suicide (2). Partially for these reasons, currently only about 13% of transgender patients undergo genital surgery for cosmetic purposes with or without gonadectomy, known as gender confirmation or reassignment surgery (GCS) (3). While some patients elect to forgo gender confirmation surgery voluntarily, others who do desire it are hindered due to cost, availability of trained providers, or the challenges in meeting the WPATH (World Professional Association for Transgender Health) guidelines for transitioning. Patient satisfaction following surgery is high, particularly regarding sexual and cosmetic outcomes; however, unexpected negative functional outcomes such as bowel and bladder dysfunction and sexual impairment can impact overall patient satisfaction (4,5).

Male-to-female genital surgery typically includes bilateral orchiectomy, penectomy, urethroplasty, labioplasty, and creation of a neovagina and neoclitoris. This can be done in one or two stages with the potential for additional reconstructive procedures in the future. Of the various vaginoplasty techniques available, the type most commonly performed involves vaginoplasty using penile skin inversion and clitoroplasty utilizing the glans penis and preserved neurovascular bundle. Other vaginoplasty techniques involve use of bowel, skin, or cheek mucosal graft. The penile portion of the urethra is amputated, followed by excision of posterior corpus spongiosum and marsupialization of the distal urothelium to the anterior skin flap (1). Bleeding and stenosis of the urethral meatus are complications associated with this approach to urethroplasty (6–9). Subsequent follow-up of patients has shown an increased risk for voiding dysfunction, abnormal urinary stream, incontinence,

and overactive bladder during both the immediate and long-term postoperative period (6,7,9–11). Thus far, postoperative urologic evaluations of MTF patients are based on retrospective analysis, single-provider samples, and simple urologic questionnaires that have no validation within this population. A recent systematic review noted that the majority of literature on outcomes was low to intermediate quality with poor comparability due to differences in data collection and surgical technique (12). The available information suggests that 16-33% of patients experience incontinence postoperatively, with stress predominance, 32-47% experience abnormal voiding, and 24-66% experience overactive bladder symptoms (10,13,14).

Outside of the typically assessed voiding symptoms, unique complaints of MTF postoperative patients include obstructive voiding symptoms due to urethral stenosis, persistent perimeatal erectile tissue, and prostatic hypertrophy (6,8,11). Unfortunately, these conditions cannot accurately be evaluated using standard urogynecologic tools, and they have not been thoroughly characterized in prior studies regarding their severity, effect on voiding, and optimal treatment strategies.

Other unique aspects of MTF patients with urologic complaints include the high dose hormonal treatments and unique neovaginal flora. The male urethra and bladder contains both alpha and beta estrogen receptors (15). Given the continuous systemic exogenous estrogen exposure, one can theorize that these receptors become activated promoting a cascade of change. This, in conjunction with an altered microbiome due to exposure to different flora after surgery, can lead to an alteration in the histology and physiology of the bladder and urethra. Anatomically, the creation of a neovagina in a previously non-occupied space below the urethra and bladder can trigger bladder irritation by mass effect, theoretically leading to the overactive bladder symptoms and voiding changes reported by some. Depending on the tissue source, the unique flora of the neovagina can seed the lower urinary tract structures, thus potentiating a reactive, potentially irritative, process.

Additionally, it has been estimated that about 8% of patients will have symptomatic neovaginal prolapse, and many will require corrective surgery (13). This is likely an underestimation as the follow-up rates for patients tends to be very low, and the lack of adequate support mechanisms for the neovagina preclude it to descend more easily than a natural vagina.

We suggest that further clarification regarding MTF postoperative urologic and pelvic floor complaints can be achieved via a mixed methods approach. By using focus group interviews to create specific evaluative questions for this unique population, we can then prospectively assess patients undergoing surgery and be more proactive in addressing their needs. A unique patient-reported outcome (PRO) questionnaire will additionally allow this patient group to feel supported and involved in their own care. In all, this will enhance the quality of our care, patient satisfaction, and success of their gender confirmatory process.

Hypotheses:

Stage 1 Unit of Analysis: To understand the urologic and pelvic floor symptoms transgender women experience following genital surgery

Stage 2 Null Hypothesis: Male-to-female gender confirmation surgery has no impact on urologic and pelvic floor symptoms including overactive bladder symptoms, incontinence, voiding dysfunction, sexual dysfunction, and prolapse.

Methodology:

Research design:

This will be a mixed methods study in an exploratory sequential design structure involving qualitative analysis via focus groups comprised of postoperative transgender women (Stage 1), followed by the distribution and testing of a questionnaire packet to male-to-female patients planning to undergo GCS at academic transgender care centers in the United States (Stage 2). The intent of the Stage 1 focus group questions will be to clarify the presentation and severity of urogynecologic symptoms in this patient group. Moderators will also ask the participants about the type and timing of their gender confirmation surgery, additional procedures, use of hormonal therapies, and neovaginal care. Please review attached Moderator Guide for the concepts to be addressed. The themes and categories generated from the focus groups will be used to create a unique screening questionnaire for this patient population that will be tested for reliability and validity in the Stage 2 component. We estimate that about 3 to 4 focus groups will be required to reach data saturation; however, additional groups may be necessary.

Stage 2 will be conducted in coordination with participating academic medical centers with affiliated gender surgeons or internal transgender care centers with surgical providers. After patient recruitment, postoperative questionnaires will be distributed which will be comprised of the Pelvic Floor Distress Inventory-20 (PFDI-20), Pelvic Floor Impact Questionnaire-7 (PFIQ-7), WHO Quality of Life BREF (WHOQOL-BREF), and the new questionnaire created from the Stage 1. We estimate about 10 minutes will be required to complete the entire questionnaire packet. A test-retest reliability challenge will be performed two weeks later with the new questionnaire only. Patient data and questionnaire answers will be entered into a universal RedCap database. All data will be analyzed at Weill Cornell Medicine. Operative information for Stage 2 participants as well as postoperative exams and treatments will be reviewed at the time of data collection and entered for analysis.

Patient recruitment for Stage 1 will be facilitated by provider referrals through transgender clinics and LGBTQ centers as well as flyer distribution to local support groups and networks (Appendix 1). A website URL (Appendix 2) will be included on the flyer for additional participation information for both Stage 1 and Stage 2.

During the focus group sessions, patients will be consented and reminded of confidentiality rules. In the advent that any disclosed information requires

immediate medical or supportive care, the participant will be placed in direct contact with their primary provider for further assistance. This will be explicitly written in the consent form and verbally announced prior to the start of the focus group. Focus group participants will be provided with a light meal and round trip Metrocard® for travel reimbursement.

There will be a separate informed written consent for Stage 2 participants. These will need to be reviewed and authorized by each participating institution prior to distribution.

Participants:

Male-to-female transgender patients who have either undergone or plan to undergo gender confirmative genital surgery.

Stage 1: In-person focus groups comprised of MTF postoperative patients who participate in support groups in various New York City LGBTQ centers. Participants will be selected using homogeneous sampling methods. We will also reach out to online support communities to set up virtual focus groups or phone interviews if feasible. We plan to embed snowballing sampling to permit recommended individuals to participate.

Stage 2: Patients scheduled to undergo gender confirmative genital surgery or recently completed surgery within academic transgender medicine centers in the United States. They will be recruited on a rolling basis.

Sample size/power:

- Stage 1: Three to four in-person/online focus groups, comprising 10-12 participants with possible one-on-one phone interviews until data saturation reached
- Stage 2: Estimated 100-150 patients (approx 10 patients per question)

Inclusion criteria:

- Stage 1 -- Male-to-female transgender women who are at least 4 weeks postoperative following genital surgery for gender confirmation
- Stage 2 -- Male-to-female transgender women who are scheduled to undergo surgery or are within 4 weeks postoperative
- Both stages -- Minimum age 18 years old
- Both stages -- English fluency
- Both stages -- Reliable contact information and/or permanent residence

Exclusion criteria:

- Preexisting pelvic pathology, including abnormal anatomy or baseline voiding dysfunction
- Urinary or intestinal problems prior to surgery lasting greater than 6 weeks

Primary outcomes:

- Stage 1: Characterization of genital, urologic, bowel, and sexual symptoms following male-to-female gender confirmation surgery
- Stage 2: Validity and reliability testing of new questionnaire

Secondary outcomes:

- Frequency and severity of symptoms
- Relationship between surgical technique and symptoms
- Effect of hormonal therapy usage and symptoms
- Length of time since surgery and development of symptoms

Confounding factors:

Patient age, race/ethnicity, weight, procedure technique, presence of non-iatrogenic causes of symptoms, co-morbidity, mobility restrictions, medication interactions, diet, infection, type and duration of hormonal therapy, prostate size, sexual activity

Research setting:

Focus groups will take place at the Lesbian, Gay, Bisexual and Transgender Community Center on [name].

Stage 2 will be conducted at various academic centers within the United States.

Committed programs include Boston Medical Center and Weill Cornell Medicine.

Study team members will reach out to additional programs at national conferences and through established networks.

All data will be collected and analyzed within Weill Cornell Medicine

Study instruments:

ATLAS.ti qualitative data analysis software (Berlin, Germany)

PFDI-20 (Pelvic Floor Distress Inventory-20)

PFIQ-7 (Pelvic Floor Impact Questionnaire-7)

WHOQOL-BREF (permission for use granted)

Data collection parameters:

DEMOGRAPHICS/ PRE-TREATMENT DETAILS

- Age
- Race/ethnicity
- Height
- Weight
- BMI (body mass index)
- Smoking status
- Sexual activity
- Medications
- Date of surgery
- Type and extent of hormonal therapy usage
- Additional genital surgical procedures

- History of preoperative urologic complaints
- History of prostatic hypertrophy or prostate cancer

POST-TREATMENT DETAILS

- Operative technique
- Complications
- Postoperative care
- Resumption of hormonal therapy
- Urinary tract infections
- Sexual activity
- Medications

Qualitative data analysis:

- Stage 1: transcript coding with thematic analysis
- Stage 2: Continuous variables will be calculated using student's t- test
 - Categorical data and outcomes will be calculated using chi-square analysis
 - Multiple regression analysis will be performed to assess for a correlation between symptomatology and operative technique, hormonal therapy, or demographics
 - The new questionnaire reliability will be challenged with internal consistency testing and 2-week test-retest
 - Construct validity will be challenged with face validity and convergent validity using the other questionnaires

Ethical issues:

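### Stage 2 sets no time after surgery for the 2-week test-retest pair and collects no rating of change, so recovery and measurement error could not be told apart if pairs fall early

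*Combined protocol and SAP*

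**What the plan says.** The Stage 2 inclusion criterion is "Male-to-female transgender women who are scheduled to undergo surgery or are within 4 weeks postoperative", and recruitment is rolling. Under Methodology, Research design: "After patient recruitment, postoperative questionnaires will be distributed". The packet holds three existing instruments and the new questionnaire; no week or month after surgery is given. The same section continues: "A test-retest reliability challenge will be performed two weeks later with the new questionnaire only".

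The Stage 2 analysis, under Qualitative data analysis, says: "The new questionnaire reliability will be challenged with internal consistency testing and 2-week test-retest". It names no coefficient, no stability rule and no subset of unchanged women. Validity and reliability testing is the Stage 2 primary outcome.

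The date of surgery, complications, urinary tract infections and medications are on the data collection list, and "Operative information for Stage 2 participants as well as postoperative exams and treatments will be reviewed at the time of data collection". None of these is tied to the retest interval.

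**The concern.** A test-retest coefficient measures reliability only if the thing measured stays the same between the two occasions. Here the first test may fall in the first weeks after genital surgery, and two weeks is the whole interval. If symptoms move in that time, part of what is scored as unreliability is recovery.

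The plan treats time as an open question. A secondary aim reads "To understand the temporal impact on symptomatology after surgery", and a secondary outcome is "Length of time since surgery and development of symptoms". The retest assumes that time has no effect over two weeks.

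One component of the primary outcome is at stake. A low coefficient could mean a poor questionnaire or a good one used during recovery, and the planned data would not show which. Internal consistency and convergent validity use a single occasion and are not affected.

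**Working it through.** **The plan's own figure.** The only Stage 2 design figure is 100-150 patients at about 10 per question, which implies 100/10 = 10 to 150/10 = 15 questions. The number of questions is not stated, so this cannot be checked further. There is no reliability target and no separate retest sample size.

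**Timing.** A woman enrolled 0-4 weeks after surgery and tested at enrolment is retested at 0+2 = 2 to 4+2 = 6 weeks. The text permits this. It also permits later pairs: a woman enrolled before surgery may be tested at any time after it.

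**Illustration.** Every value below is an assumption. True scores have variance 1. With a true ICC of 0.85, error variance is 1/0.85 - 1 = 0.176. A share p of pairs has true change with mean m and SD s, in true-score SD units and independent of the starting level; the rest have none.

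- Agreement ICC = 1 / (1.176 + p(m² + s²)/2)
- Consistency ICC = 1 / (1.176 + [p s² + p(1-p) m²]/2)

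For p = 1 and m = s = 0.5, agreement is 1/(1.176 + 0.25) = 0.70 and consistency is 1/(1.176 + 0.125) = 0.77.

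| Share early | Coefficient | 0.3/0.3 | 0.5/0.5 | 0.5/0.7 |
|---|---|---|---|---|
| All | Agreement | 0.79 | 0.70 | 0.65 |
| All | Consistency | 0.82 | 0.77 | 0.70 |
| Quarter | Agreement | 0.83 | 0.81 | 0.79 |
| Quarter | Consistency | 0.84 | 0.81 | 0.79 |

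(Columns are m/s.) With s = 0 and p = 1, consistency stays at 0.85: a uniform shift lowers only the agreement coefficient.

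**Against sampling error.** The F-based 95% interval for an ICC of 0.85 with 100 pairs is 0.785 to 0.897. The agreement ICC falls to 0.785 when p = 2(1/0.785 - 1.176)/(m² + s²). This is 1.08 (impossible), 0.39 and 0.26 for the three cases.

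**Offset.** If early recovery also spreads women apart, reliability rises. Adding 0.25 to the between-women variance with all pairs early gives an agreement ICC of 1.25/(1.426 + 0.09) = 0.82 at 0.3/0.3, 0.75 at 0.5/0.5 and 0.70 at 0.5/0.7. Without change it would be 1.25/1.426 = 0.88.

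**Would a change rating find the unchanged women?** In simulation, the rating equals true change, plus a fraction c of the questionnaire's error difference, plus independent noise of SD r. A woman counts as unchanged if her rating is within 0.3 of zero. With all pairs early and independent error only (c = 0, r = 0.3 to 0.5), the agreement ICC in that subset is 0.78-0.82. With shared error (c = 0.5, r = 0.3) it is about 0.91, and it is 0.91 even with no true change at all. The subset keeps 22-42% of pairs if all are early and 38-55% if half are (r = 0.3). The 95% interval around 0.85 is 0.71-0.93 with 30 pairs and 0.75-0.91 with 50.

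**The case against.** The strongest reply is that early pairs are only permitted. The 4-week limit governs enrolment, not the timing of the packet, and women enrolled before surgery may be tested much later. Symptoms reported in both the immediate and long-term periods do not show change over two weeks. This stands, and it is why harm is not claimed.

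Second, the effect depends on the coefficient, and the plan names none. At 0.5/0.5 with all pairs early, agreement falls by 0.15 and consistency by 0.08, so almost half of the larger drop comes from the choice of coefficient. This also stands, and it is a reason to name one.

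Third, the bias is conservative: in this model, change makes the questionnaire look worse, whereas the self-rated unchanged subset can look better than the truth. This stands and limits the subset to a sensitivity analysis.

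Fourth, data already collected could flag some women who changed. That is true in part, but no such use is planned, and none of these items measures symptom change over the two weeks.

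Two stronger readings are tempting. A reader might infer that all true change counts as error; that fails for a uniform shift under a consistency or Pearson coefficient. A reader might also infer from the Stage 1 criterion, "Male-to-female transgender women who are at least 4 weeks postoperative following genital surgery for gender confirmation", that the plan regards earlier weeks as unstable. It is an eligibility rule for the focus groups, and the documents give no such reason for it.

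**Conclusion.** The gap is real: no time since surgery is fixed for the pair, and no planned measure or analysis distinguishes women whose symptoms changed from those whose symptoms did not. Its effect is conditional on pairs falling early and on symptoms then changing over two weeks. If a quarter of pairs are early, the assumed changes lower the agreement ICC from 0.85 by 0.02 to 0.06; if all are, by 0.06 to 0.20. The smallest assumed change never takes it outside the interval expected with 100 pairs. These figures rest on an assumed true ICC, assumed change sizes and change independent of starting level; extra spread between women would offset part of the drop. Severity is minor to moderate. The case for acting is that the rating is cheap and cannot be collected once the retest is over.

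**What to change.** 1. Add one global rating-of-change question to the 2-week retest: since the last questionnaire, are symptoms better, the same or worse.
2. Name the ICC and its type (two-way absolute agreement would be reasonable) and keep the all-pairs value as the main reported estimate. Show the ICC in women who report no change only as a sensitivity analysis. Say that shared self-report error can inflate it, that it rests on fewer pairs, that a gap between the two does not prove true change, and that the two values need not bracket the truth.
3. Report test-retest reliability by time since surgery, using the date of surgery already collected.
4. State when after surgery the first questionnaire is given and, once the questionnaire is built, its recall period.

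The cost is one question per woman and a short analysis statement. Item 3 needs no new data and no new scheduling across sites. The main drawback is the smaller, imperfect subset.

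### Stage 2 admits women before surgery and up to four weeks after it, but no planned analysis uses entry route, so reported symptom frequency can be biased in either direction

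*Combined protocol and SAP*

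**What the plan says.** The document describes the Stage 2 population in more than one way.

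- Participants: "Patients scheduled to undergo gender confirmative genital surgery or recently completed surgery within academic transgender medicine centers in the United States".
- Inclusion criteria: "Stage 2 -- Male-to-female transgender women who are scheduled to undergo surgery or are within 4 weeks postoperative".
- Methodology, Research design: "distribution and testing of a questionnaire packet to male-to-female patients planning to undergo GCS at academic transgender care centers". This covers women before surgery only.
- Background/significance, closing rationale: "we can then prospectively assess patients undergoing surgery and be more proactive in addressing their needs".

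On recruitment, the Participants section says "They will be recruited on a rolling basis". The Research design section adds "A website URL (Appendix 2) will be included on the flyer for additional participation information for both Stage 1 and Stage 2". On measurement, it says "After patient recruitment, postoperative questionnaires will be distributed", with no time point.

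The first secondary outcome is "Frequency and severity of symptoms". The Stage 2 primary outcome is validity and reliability of the new questionnaire. The analysis section lists t-tests, chi-square tests, and a multiple regression of symptoms on technique, hormonal therapy or demographics. Neither that section nor the list of confounding factors mentions whether a woman enrolled before or after her operation. Time since surgery is a secondary outcome, but that concerns when symptoms develop, not when the woman joined.

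**The concern.** The two routes differ in what a woman can know when she decides to take part. Before surgery, no postoperative symptom exists, so entry cannot depend on one. In the four weeks after surgery, some women will have early symptoms, and these may make them more willing to answer a symptom questionnaire or, if they are unwell, less willing. Entry by the second route can then depend on the outcome being counted.

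If the routes are combined, the reported frequency reflects who joined as well as how common symptoms are, and a larger sample does not reduce that error. If one technique contributes more postoperative entrants than another, part of any difference between techniques could come from the same source. The background section criticises earlier work for retrospective analysis and single-provider samples, so an unexamined selection effect would weaken an estimate meant to improve on it.

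**Working it through.** **The plan's own figure.** The Stage 2 target is 100-150 women at about 10 per question. That implies 100/10 = 10 to 150/10 = 15 questions. The number of questions is not stated, so the figure is consistent but cannot be reproduced independently. It is a rule for validation and sets no precision for a frequency.

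**Inputs.**
- p, true frequency: 32%, the low end of the background section's range for abnormal voiding (32-47%), used only as an illustration.
- q, share of enrolled women who entered after surgery: not in the documents; assumed 25%, 50% or 75%.
- r, probability of entry for symptomatic relative to asymptomatic women in the postoperative route: not in the documents; assumed 0.67 to 3.

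**Formulas.** Frequency among postoperative entrants: P_post = r·p / (r·p + 1 − p). Pooled frequency: (1 − q)·p + q·P_post.

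**Example, r = 2.** P_post = 0.64 / (0.64 + 0.68) = 0.64/1.32 = 48.5%. With q = 50%, pooled = 0.5 × 32 + 0.5 × 48.5 = 40.2%.

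**Example, r = 0.67.** P_post = 0.2144 / (0.2144 + 0.68) = 24.0%. With q = 50%, pooled = 28.0%.

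| r | Postoperative entrants | Pooled, q = 25% | Pooled, q = 50% | Pooled, q = 75% |
|---|---|---|---|---|
| 0.67 | 24.0% | 30.0% | 28.0% | 26.0% |
| 1 | 32.0% | 32.0% | 32.0% | 32.0% |
| 1.5 | 41.4% | 34.3% | 36.7% | 39.0% |
| 2 | 48.5% | 36.1% | 40.2% | 44.4% |
| 3 | 58.5% | 38.6% | 45.3% | 51.9% |

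**Other symptoms.** Using the ends of the background ranges for incontinence (16-33%), abnormal voiding (32-47%) and overactive bladder (24-66%), the bias at r = 2 and q = 50% is +5.8 to +8.5 points. At r = 0.67, over q = 25-75%, it is −1.2 to −7.3 points.

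**Technique comparison.** Suppose two techniques both have a true 32%, r = 2, and 25% and 75% postoperative entry. From the table, they would show 36.1% and 44.4%, an apparent difference of about 8 points with no true difference.

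**Precision.** The 95% half-width is 1.96·√(p(1 − p)/n). At p = 32% it is 91.4/√n points.
- Full sample: 9.1 points at n = 100 and 7.5 at n = 150.
- Half in each route (50-75 women): 12.9 and 10.6 points.
- One quarter in a route (25-38 women): 18.3 and 14.8 points.

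The bias at r = 2 and q = 50% (8.2 points) is thus about as large as the sampling error of the full sample.

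**Would a test between routes settle it?** With equal routes and r = 2, a two-sided 5% test has about 29-54% power across true rates of 16-66% and totals of 100-150. A non-significant difference would not rule the bias out.

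**The case against.** The strongest reply is that the Stage 2 primary outcome is psychometric and does not need unselected entry, so this is an unquantified risk to a descriptive secondary outcome. The documents give neither q nor r, and at r = 1 there is no bias. The window is at most four weeks, so symptoms that appear later, as prolapse or sexual dysfunction may, cannot drive entry. The 32% comes from published follow-up studies, one of them titled as 16 years after surgery, so it may not describe the early symptoms that could affect joining. Pooling is inferred, because the plan never says the routes will be combined. All of this stands. It limits the size and priority of the point but does not remove the gap.

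A reader might also infer several stronger things that the documents do not support:

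- *That enrolment is not consecutive.* Rolling recruitment describes timing and is compatible with approaching every eligible patient.
- *That Stage 2 recruits through publicity about postoperative problems.* Flyers and referrals are described for Stage 1. The flyer only carries a web address with information on both stages, and its content is not available.
- *That the exclusions for earlier problems rest on recall in one route and on direct questioning in the other.* How they are ascertained is not stated; records could serve both.
- *That postoperative entrants' symptoms are already known at entry.* Some may be present; later ones cannot be.
- *That the bias is usually upward.* Nothing in the documents fixes its direction.

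**Conclusion.** The point holds as a modest one. Two entry routes are explicit, the outcome is measured after surgery, and no stated analysis or listed confounder separates the routes. Symptom frequency and severity can therefore be biased in either direction, and the technique comparison too if the mix of routes differs by technique. Validity and reliability are less affected, although a changed symptom mix could shift their coefficients.

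At a true 32% with half entering after surgery, the illustration gives 28% to 40% as r runs from 0.67 to 2. This rests on assumed q and r, and on early symptoms being related to those later measured. It shows what could happen and does not estimate what will.

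A reader might conclude that women enrolled before surgery should supply the only primary frequency estimate. The documents do not compel that. With three quarters entering after surgery, 25-38 women would remain. They must also return a postoperative questionnaire, and the background section itself describes follow-up as tending to be very low. That group is free of symptom-driven entry but not of selective non-response.

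**What to change.** 1. Reconcile the Research design section with the Participants section and inclusion criteria, so that the Stage 2 population is defined once.
2. Record consent date beside date of surgery and derive entry route. Only date of surgery is in the listed data collection parameters; consent must precede questionnaire completion, so the date is easy to capture. If de-identification is a difficulty, store the interval from surgery to consent.
3. Use all women for validity and reliability.
4. Report symptom frequency and severity for women who consented before surgery and for those who consented after it, with intervals, beside the pooled figure. Describe the first as free of symptom-driven entry, and give its questionnaire response rate. Do not use a significance test between routes to justify pooling.
5. Add entry route to the technique and hormone regression. In the working, selection multiplies the odds of a symptom by r, so a route term in a logistic model absorbs it if r is the same for every technique; otherwise the correction is partial.

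The cost is one data field, one regression term and wider intervals by route: at 32%, about 11-13 points with 50-75 women and 15-18 points with 25-38, against 7-9 for the full sample. No woman is lost and the recruitment target is unchanged.
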